6.5 Period of Follow-Up after ES

After 1 month of ES and motor training, each subject will be asked to complete two follow-up assessments at time points 1 month and 4 months after completing the intervention to monitor changes in primary and secondary outcome measures. Subjects will be asked to refrain from partaking in additional therapies or interventions with the goal of improving functional measures related to their SCI during this 4-month follow-up period.

6.6 Outcome Measures

The following outcome measures will be collected as scheduled in **Table 3** with tests occurring over an approximately one-week period of time for each time point. Photographic and video images will be recorded throughout the study, but will not be shown to anyone outside the study team without the subject's written consent.

6.6.1 Primary:

Biomechanical assessments

During a variety of tasks including supine, side-lying, reaching, standing, and stepping activities, kinematics, EMG, and foot pressure measurements may be obtained, with or without spinal stimulation, using the following metrics:

Kinematics: We will use commercially available_markers placed on the skin surface via a non-irritant adhesive to record limb movement and joint angles. Available systems we may use include video-based, inertial measurement units, electromagnetic.

Electromyography: We will collect muscle activity using skin surface electrodes placed at anatomical locations of muscle groups below the level of injury. Activity will be recorded using a 16-channel signal amplifier and data acquisition system (PowerLab, ADInstruments, Colorado). At locations where self-adhesive bipolar recording electrodes will be placed onto the skin, the area will be cleaned with alcohol to ensure secure attachment and enhance signal recordings. A subset of the following muscles or muscle groups will be tested: soleus, gastrocnemius, tibialis anterior, hamstrings, quadriceps, hip adductors, gluteus maximus, gluteus medius, abdominals, triceps, trapezius, and spinal extensors.

Foot pressure: Foot pressure will be measured with shoe-insole pressure sensors (F-SCAN, Tekscan Inc., Boston, MA).

Seated pressure: Seated pressure will be assessed via a force sensing array placed beneath the buttocks (Vista Medical BodiTrak force sensing array, Winnipeg, MB, Canada).

Over the course of rehabilitation, if the research team observes stimulation-enabled functions that could be enhanced by further optimization of stimulation parameters, biomechanical assessment equipment may be used during select rehabilitation sessions in addition to the main assessment timepoints described in **Table 3**.

Table 3: Outcom	e Measure	es								
			Stı	ıdy Tin	neline					
	Screening	Pre	Implant	Spinal Stimulation + Motor training			Explant	Post	Follow-Up	
Weeks	0	Baseline		1	2	3	4		5	8, 20
Motor Training				X	X	X	X			
Urinalysis	X									
DEXA ¹	X									
		P	rin	nary Ou	ıtcome	es				
Kinematics ²				X			X			X
EMG ²		X		X			X		X	X
SSEPs		X							X	X
TMS MEPs		X							X	X
TMS + ES or TS2		X							X	X
TS MEPs	X								X	X
ES MEPs				X			X			
BBS, TUG, 6MWT		X							X	X
FRT/mFRT				X			X			X
ISNCSCI	X								X	X
Secondary Outcomes										
Spine CT or MRI	X			X			X			
Urodynamic Studies		X							X	
Surveys		X							X	X

^{1.} DEXA scan measured at either left or right femur, and AP spine; not to include total body scan.

DEXA=Dual Emission X-ray Absorptiometry, EMG=Electromyography, SSEPs=Somatosensory Ewoked Potentials, TMS=Transcranial Magnetic Stimulation, MEPs=Motor Evoked Potentials, ES=Epidural Stimulation, TS=Transcutaneous Stimulation, BBS=Berg Balance Score, TUG=Timed Up and Go, 6MWT=6 Minute Walk Test, mFRT=Modified Functional Reach Test, ISNCSCI=International Standards of Neurological Classification of Spinal Cord Injury

^{2.} Further optimization may occur during training weeks 1-4.

Electrophysiology tests

Somatosensory evoked potentials (SSEPs): SSEPs will be recorded through surface electrodes to measure conduction in the peripheral nerves, cervical and lumbosacral spinal cord, deep brain structures, and sensory cortex. Skin will be cleaned with alcohol and prepared using mild abrasive tape for placement of surface electrodes. For tibial recordings the tibial nerve will be stimulated behind the medial malleolus with recordings on the scalp utilizing a Fz,-CZ montage (International 10-20 System for EEG electrode placement), the cervical spine (C5 reference to Fz), the L1 spine (referenced to iliac crest), and the popliteal region. For median SSEPs, the median nerve will be stimulated at the wrist with recording electrodes at the scalp (C3-C4), the cervical spine (C5-Fz), Erb's point (referenced to contralateral Erb's) and the elbow. Repeated single-pulse electrical stimulation will be delivered at intensities of 1-1.5 times motor threshold for visual twitch for each of the four nerves evaluated. Averaged responses for up to 256 stimuli will be recorded for each of these two intensities for the right and left median and tibial nerves. Simultaneous bilateral stimulation will be applied if no recognizable responses are recorded from the scalp leads. Stimulation delivery rates will not exceed 2 per second. Recorded data will include amplitudes, peak latencies and interpeak latencies. Existing SSEPs within 6 months of screening may be acceptable for Baseline results at the investigators' discretion.

Transcranial magnetic stimulation (TMS) Motor evoked potentials (MEP): TMS MEPs will be evoked by placing a magnetic coil over the vertex of the head to elicit MEP. Upper limb MEPs will be recorded from the deltoid, triceps brachii, flexor carpi radialis and abductor pollicis brevis using the EMG system described in the biomechanics testing. The "threshold" TMS intensity will be defined as the minimum stimulus intensity required to elicit a response, recorded from muscles above the injury, that appears in response to >50% of the stimuli pulses delivered. If no MEPs are observed in EMG recordings from muscles that are innervated by the spinal cord below the level of injury, but are present in muscles innervated by spinal segments above the injury, then the injury severity will be deemed functionally motor complete. Data will be digitized, and MEPs responses averaged for each muscle. Latencies (interval from stimulus artifact to onset of response) and peak-to-peak amplitudes of MEPs responses will be assessed from all muscles. Existing TMS-MEPs within 6 months of screening may be acceptable for Baseline results at the investigators' discretion.

TMS Pulses Paired to TS or ES Pulses

In order to interrogate the corticospinal connectivity which may be responsible for transmitting volitional motor commands during TS and/or ES through the injury site in participants with SCI, we will apply pulses of TMS at time intervals ranging from 5-100ms prior to activation of lumbosacral spinal circuitry via pulses of either TS or ES. Evidence suggests both TS and ES, applied over the thoracolumbar spine, activate dorsal roots to elicit a motor reflex root-evoked potential. At each assessment time point, we will incrementally increase TS or ES pulse amplitudes to identify the stimulus intensity that consistently generates spinal reflex activity recorded via lower extremity EMG. Then, two TS or ES pulses will be delivered 50 ms apart to characterize the transsynaptic nature of the reflex which will be determined by observing suppression of a

response to the second stimulus pulse (i.e., post activation depression). Next, we will examine the conditioning effect (e.g., no change, increased amplitude of reflex, or decreased amplitude of reflex) of delivering TMS pulses at time intervals ranging from 5-100ms prior to pulses of TS or ES while recording spinal circuitry outputs via lower extremity EMG.

TS MEPs

To assess the functional states of the spinal circuitry, we will deliver transcutaneous spinal stimulation via pulses of 1 ms duration at intensities of up to 100 mA. Stimulation will be delivered to multiple locations of the lumbosacral region with participants in a supine position. Evoked potentials will be recorded via surface EMG electrodes placed bilaterally over the soleus, gastrocnemius, tibialis anterior, hamstrings, quadriceps, hip adductors, gluteus maximus, gluteus medius, abdominals and spinal extensors. We will record evoked potentials while relaxed using stimulus intensities from 1-100 mA at increments of 10 mA for each stimulus location. Evoked potentials for each stimulus location and intensity will be averaged and visualized in real-time to determine the optimal location for evoking threshold potentials across all recorded muscles. Stimulus intensities that are at the threshold for evoking motor potentials will be delivered: while attempting prolonged maximal contractions of all muscles; during attempts to contract the left leg; and during attempts to contract the right leg. Evoked potentials will be analyzed according to task, stimulus intensity, and stimulus location.

ES MEPs

To assess the effects of delivering ES pulses to various regions of the lumbosacral spinal cord, we will record skin surface EMG from lower extremity muscles while ES is delivered to the temporarily implanted electrodes using a subset of anode/cathode configurations. Electrode configurations will be selected in order to selectively stimulate the rostral or caudal regions of the spinal cord within the T11-L1 vertebral bodies. This region of the spinal cord innervates the left and right proximal or distal muscles of the left/right lower extremities. ES pulses will be delivered as biphasic charge-balanced rectangular pulses ranging in pulse width (0.05-1ms), amplitude (0-25.5mA), and frequency (0.5-200 Hz). Within the implanted lead, each electrode could be configured as a cathode, anode, or off, and individual electrode configurations in order to target specific rostral-caudal and medial-lateral regions of the spinal cord to generate specific motor outputs.

Overground mobility

For subjects with motor incomplete injuries, attempts to stand and generate steps with varying degrees of body-weight support will be assessed using the Timed Up and Go (TUG), Berg Balance Score (BBS) while using the 6 Minute Walk Test (6MWT) to assess endurance changes. Measurements made as part of intake for the SCI Service Line may be used, if available.

Balance Assessment

A motion capture camera system will be used to assess trunk stability according to the protocol from the modified functional reach test (mFRT) for subjects unable to stand. The subject will be outfitted with reflector markers on specific upper limb, trunk, pelvic, and lower limb landmarks. This procedure will consist of the subject sitting with hips, knees, and ankles position at 90 degrees of flexion with feet positioned flat on the floor. The subject is then asked to reach forward and laterally with their upper extremities while maintaining trunk stability. The extent to which the subject can reach before trunk balance becomes unstable (requiring assistance to regain balance from the physical therapist) is measured for multiple reaching trials.

During the trunk stability assessment, skin surface EMG will be collected bilaterally from lower extremity and trunk muscles, as well as the trapezius. Pressure recordings will also be collected from under both feet and under the buttocks.

Subjects capable of standing will undergo assessment via Berg Balance Assessment, the standing version of the Functional Reach Test (FRT), and the modified functional reach test (mFRT).

International Standards of Neurological Classification of SCI (ISNCSCI)

We will conduct ASIA Impairment Scale (AIS) to assess severity of the injury. This test focuses mainly on sensory and motor functions. Measurements made as part of intake for the SCI Service Line may be used, if available.

6.6.2 Secondary:

Spine Imaging

Baseline CT of the spine will be used to evaluate the structural integrity of the spine prior to study onset, and to visualize spine fusion hardware with respect to TS location and preparation of ES implantation location. Baseline spine MRI will be used to evaluate injury severity and assess potential of spared tissue (discomplete SCI) despite complete loss of motor function. Spine CT will be repeated for subjects following ES implantation to visualize array location, and at the end of the study to evaluate changes in array location. Existing spine CTs and MRI within 6 months of screening may be acceptable for Baseline results at the investigators' discretion.

Over the course of rehabilitation sessions with ES, one additional x-ray may be performed to visualize the location of implanted leads. This x-ray will be performed if stimulation-enabled motor activity is remarkably inconsistent from session to session, which might indicate migration of the ES lead(s).

Bladder function

A urodynamic test consisting of a filling phase and a voiding phase cystometrogram along with perineal patch muscle electromyography (EMG) will be performed with the stimulator both on and off. Specifically, a 9F double-lumen catheter will be introduced transurethrally into the bladder. One lumen of this catheter will be used for bladder filling at an average flow rate of 20-25 ml/min (according to ICS guidelines), and another will record intravesical pressure. Intra-abdominal pressure will be recorded by a 12F rectal catheter. Through multichannel pressure transduction, intravesical and intra-abdominal pressures will be simultaneously

transduced on a strip chart recorder. Detrusor pressures will be simultaneously calculated by subtracting vesical from abdominal pressures. Sphincter EMG activity is observed by using patch electrodes. Existing urodynamic studies within 6 months of screening may be acceptable for Baseline results at the investigators' discretion.

Surveys

A battery of clinical surveys will be captured to assess subjects' assessment of quality of life, and health habits such as bowel and bladder function, and sexual function. Any of these surveys done as part of intake for the SCI Service Line may be used, if available.

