This study will include adult humans that sustained a traumatic SCI at least one year before trial enrollment. To qualify for this study, SCI severity must be previously diagnosed with an AIS classified injury. One participant will be enrolled from each AIS classification (A, B, C, and D) for each intervention. All injuries must be located at or above the tenth thoracic vertebrae. Detailed inclusion and exclusion criteria are provided within the appropriate section of this protocol.

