4.3 Subject Recruitment, Enrollment and Screening

A total of 8 subjects will undergo the experiments described within this protocol. Subjects will be recruited from the following:

- Mayo Clinic's volunteer research subject database
- Mayo Clinic's clinical trials website
- Mayo Clinic's electronic medical record database search tools
- ClinicalTrials.gov

Prior to participating in the screening phase, a member of the research team will provide a detailed explanation of the study and answer questions asked by the potential study subject. If the potential subject is willing to participate in the study, they will be given sufficient time to make an informed decision, review relevant informed consent documents, and ask questions. Once questions and concerns have been addressed to the potential subject's satisfaction, the informed consent form will be signed and dated by the subject and an Investigator. A copy of the signed consent documents will be provided to the subject. The original signed consent documents will be retained within study records.

Following informed consent, screening tests will be performed including a thorough history and physical examination by a physician and physical therapist. Pre-existing clinical results to screening assessments may be accepted at the investigators' discretion if the testing was done within the timeframe specified for each test in the Study Procedures section. The ASIA Impairment Scale (AIS) examination will also be completed during screening to determine severity and classification of SCI. Urine tests will be completed to rule out an active urinary tract infection; if the testing is positive for a urinary tract infection, the subject will be

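### For 4 of the 10 primary-outcome rows in Table 3 the baseline may predate the study, so any change before training would be counted as change over rehabilitation

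*Combined protocol and SAP*

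**What the plan says.** The permissions are all in Section 6.6.1:

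- Somatosensory evoked potentials (SSEPs): "Existing SSEPs within 6 months of screening may be acceptable for Baseline results at the" investigators' discretion.
- Motor evoked potentials from transcranial magnetic stimulation (TMS-MEPs): "Existing TMS-MEPs within 6 months of screening may be acceptable for Baseline results at the investigators' discretion".
- Overground mobility (BBS, TUG, 6MWT), and again under ISNCSCI: "Measurements made as part of intake for the SCI Service Line may be used, if available". No maximum age and no condition on equipment or assessor is attached.

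Table 3 lists these four rows as primary outcomes. It schedules ISNCSCI at Screening and the other three at Pre.

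Other sections bear on this:

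- Section 4.3 accepts pre-existing clinical results for screening assessments only "if the testing was done within the timeframe specified for each test in the Study Procedures section". It adds that the AIS "examination will also be completed during screening to determine severity and classification of SCI".
- Section 1.1: "This study will include adult humans that sustained a traumatic SCI at least one year before trial enrollment". Section 4.1 repeats the one-year minimum.
- The opening of Section 6.6 places the tests of each time point within about one week.
- Section 5.5 sets no limit on therapy before enrolment. Its example of outside locomotor training is to be stopped only while the subject is in the trial.
- The Study Summary plans repeated measures analysis of variance for change over rehabilitation.
- Section 8.2 has no term for baseline age or time since injury, and no analysis that leaves out reused baselines.
- Both arms are stimulated (Section 8.1), allocation is by availability or the subject's choice (Section 5.2), and the study is unblinded (Section 5.7).

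**The concern.** A change from baseline can be read as change over rehabilitation only if the baseline was taken shortly before rehabilitation began. Here it may have been taken months earlier, on other equipment or by another assessor, and in some subjects before they reached the one-year mark required for entry.

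Whatever happened between that measurement and the first session then becomes part of the recorded change. Spontaneous change is one possibility. Therapy aimed at function is another, since Section 5.5 leaves it unrestricted before enrolment. A different recording set-up is a third: Section 6.6.1 specifies nerves, montage and two intensities for SSEPs and the study EMG system for TMS-MEPs, but does not say that a reused record must match.

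No untreated arm would expose such drift. Because reuse is discretionary, some subjects may have a new baseline and others an old one, and the mix may differ between arms. The misdating also reaches two further uses of baseline values: the search in Section 8.2 for predictors of response, and the aim in Section 1 of separating responders from non-responders.

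**Working it through.** The plan gives no power, alpha, standard deviation or effect size (Section 8.1), so it has no figure to reproduce. The check is date arithmetic followed by an illustration.

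**Inputs.** Minimum time since injury is 12 months (Sections 1.1 and 4.1). The reuse window is 6 months before screening (Section 6.6.1). Post is week 5 and follow-up is weeks 8 and 20 (Table 3). There are 4 subjects per arm (Section 5.2).

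**Scope.** The primary rows are kinematics, EMG, SSEPs, TMS-MEPs, TMS paired with ES or TS, TS MEPs, ES MEPs, BBS/TUG/6MWT, FRT/mFRT and ISNCSCI, which makes 10. A reuse sentence is attached to SSEPs, TMS-MEPs, BBS/TUG/6MWT and ISNCSCI, which makes 4.

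**Earliest evoked-potential baseline.** 12 − 6 = 6 months after injury.

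**Interval from baseline to assessment.** Six months is 6 × 365.25 / 12 / 7 = 26.1 weeks. Interval with an old baseline = 26.1 + Table 3 week.

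| Visit | New baseline (weeks) | 6-month-old baseline (weeks) | Ratio | Share before the study timeline starts |
|---|---|---|---|---|
| Post, week 5 | about 5 | 31.1 | 6.2 | 84% |
| Follow-up, week 8 | about 8 | 34.1 | 4.3 | 77% |
| Follow-up, week 20 | about 20 | 46.1 | 2.3 | 57% |

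The window runs from screening, so a gap between screening and the first session adds to these intervals.

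**Service-line intake values.** Section 6.6.1 gives no bound. As an illustration, a value 9 months old at entry in a subject at 12 months would date from 12 − 9 = 3 months after injury. The sentence does not use the word baseline, but an intake value cannot be a Post or follow-up value, so only the pre-training measurement can be meant.

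**Effect on an arm's mean change.** If one of 4 subjects has drift d before the study, the mean moves by d/4. The documents give no drift rate. Assuming r = 0 to 0.10 baseline SD per month over 6 months with k of 4 subjects reused, bias = 6 × r × k/4:

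| r (SD per month) | k = 1 | k = 2 | k = 4 |
|---|---|---|---|
| 0 | 0 | 0 | 0 |
| 0.02 | 0.03 | 0.06 | 0.12 |
| 0.05 | 0.075 | 0.15 | 0.30 |
| 0.10 | 0.15 | 0.30 | 0.60 |

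Section 8.2 summarises by medians. The median of four values is the average of the middle two, so drift d in one subject moves it by anything from 0 to d/2.

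Overground mobility is tested only in motor-incomplete subjects. If those are the C and D grades (an assumption), with one subject per grade per arm (Section 1.1), two subjects contribute and one drifted baseline moves the mean by d/2.

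**Difference between arms.** Bias in the ES − TS difference = (bias in ES) − (bias in TS). It is zero when drift and baseline age are alike in the two arms.

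**The case against.** The best case for the plan is that reuse is optional, the default in Table 3 is a new measurement, and the investigators can reject a record that is not comparable. The extreme case needs a subject at the eligibility limit, a test at the end of its window, and acceptance of that test. Most primary rows are untouched, including kinematics, EMG and the TS and ES evoked potentials, which bear most directly on the primary objective of activity during stimulation-enabled tasks. Comparisons of week 5 with weeks 8 and 20 do not use the baseline at all. In an eight-subject pilot reported mainly through individual plots, a reanalysis without reused baselines would be hard to interpret.

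All of this limits the scope and size of the problem. It does not remove the permission, and discretion in an unblinded study is not a rule.

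A reader might also infer more than the documents support:

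- *That natural recovery will be counted as treatment effect.* The documents give no recovery rate for this period. Only the conditional statement holds: any spontaneous change would be counted.
- *That the plan breaks its own reason for the one-year rule.* Sections 1.1 and 4.1 state the rule without a reason, and it governs entry rather than the date of each test.
- *That intake values of any age are clearly allowed.* Section 4.3 refers to a timeframe for each test, and none is given for these. It also calls for an AIS examination during screening. For ISNCSCI this is a contradiction to resolve. For BBS/TUG/6MWT, a Pre assessment, the missing limit is plainer.
- *That the ES−TS difference shifts by d/4 for each old baseline.* That holds for a mean with drift in one arm only. Drift common to both arms cancels, and a median behaves differently.

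**Conclusion.** The point holds for 4 of the 10 primary rows. For SSEPs and TMS-MEPs the baseline can come from as early as 6 months after injury in a just-eligible subject, and about 31 weeks before Post instead of about 5. For BBS/TUG/6MWT and ISNCSCI, Section 6.6.1 sets no age limit and is at odds with Section 4.3.

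The exposed quantity is the within-arm change from baseline, which the planned analysis would read as change over rehabilitation. The size of the bias is unknown and may be zero; the SD figures above rest wholly on an assumed drift rate. The TS−ES contrast is biased only if baseline age or drift differs by arm. The documents do not show that it would, but discretionary reuse and non-random allocation of four per arm do not prevent it. The change is worth making because the permission is explicit and the remedy is already in the schedule.

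**What to change.** In the four places in Section 6.6.1 (SSEPs, TMS-MEPs, overground mobility, ISNCSCI), limit existing results to screening or eligibility. State that the analysed baseline is measured on the study set-up at the Screening or Pre visit where Table 3 already places it. Reconcile the two service-line sentences with Section 4.3, both on the timeframe for each test and on the AIS examination during screening.

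If reuse is kept:

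- accept only results obtained at least 12 months after injury with a comparable set-up;
- record the date of every baseline value;
- mark reused baselines in the individual plots of Section 8.2;
- repeat the change analysis without them, as a description only given the numbers.

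The cost is wording in four places, the reconciliation with Section 4.3, and, for some subjects, repeating a non-invasive test that is already scheduled. The reuse rules for imaging and urodynamics, which are secondary outcomes, can stay as they are.
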